6.4.1.7 Assessment of Severity

The severity, or intensity, of an AE refers to the extent to which an AE affects the subject's daily activities. The intensity of the AE will be rated as mild, moderate, or severe using the following criteria:

- Mild: An AE that is transient in nature and generally does not interfere with the subject's normal activities.
- Moderate: An AE that is sufficiently discomforting to interfere with the subject's normal activities.
- Severe: An AE that is incapacitating and prevents normal activities.

Changes in the severity of an AE should be documented to allow an assessment of the duration of the event at each level of intensity to be performed. Adverse events characterized as intermittent do not require documentation of onset and duration of each episode.

6.4.1.8 Assessment of Causality

The investigator's assessment of an AE's relationship to study drug is part of the documentation process, but it is not a factor in determining what is or is not reported in the study. If there is any doubt as to whether a clinical observation is an AE, the event should be reported.

The relationship or association of the study drug in causing or contributing to the AE will be characterized using the following classification and criteria:

- Unrelated: This relationship suggests that there is no association between the study drug and the reported event.
- Possible: This relationship suggests that treatment with the study drug caused or contributed to the AE, i.e., the event follows a reasonable temporal sequence from the time of drug administration or follows a known response pattern to the study drug but could also have been produced by other factors.
- Probable: This relationship suggests that a reasonable temporal sequence of the event with drug administration exists and, based upon the known pharmacological action of the drug, known or previously reported adverse reactions to the drug or class of drugs, or judgment based on the investigator's clinical experience, the association of the event with the study drug seems likely. The event disappears or decreases on cessation or reduction of the dose of study drug.
- Definite: This relationship suggests that a definite causal relationship exists between drug administration and the AE, and other conditions (concurrent illness, progression/expression of disease state, or concurrent medication reaction) do not appear to explain the event. The event reappears or worsens if the study drug is re-administered.

6.4.1.9 Follow-Up of Subjects Reporting Adverse Events

All AEs must be reported in detail on the appropriate page in the eCRF and followed to satisfactory resolution, until the investigator deems the event to be chronic or not clinically significant, or until the subject is considered stable.

6.4.2 Other Safety Assessments

Safety assessments other than AEs (Section 6.4.1) include assessment of suicidality, collection of seizure diaries, clinical laboratory analyses (Section 6.7), vital sign measurements, and physical examinations.

6.4.2.1 Assessment of Suicidality

The ABC-I will be used to assess suicidality instead of the Columbia-Suicide Severity Rating Scale, since cognitive impairment in Angelman syndrome patients interferes with the understanding of the concept of suicide. Most individuals with AS are not able to communicate thoughts of suicidality, so the subject's irritability reported by the LAR/caregiver is being used as a surrogate measure of suicidality. The investigator will review the scale items with the LAR/caregiver at each scheduled time point. If grading worsens, the investigator must decide whether that indicates a potential for self-harm by the subject, and if so, must document it as an AE and closely monitor it until resolution. The entire Aberrant Behavior Checklist – Community (ABC-C) will be administered although only the ABC-I will be used to assess the potential for self-harm.

6.4.2.2 Seizure Diary

The seizure diary is a caregiver-reported clinical outcome assessment measure that captures the total number and duration of seizures. Caregivers will record the number, duration, and type of seizures each day using the paper seizure diary. Also, refer to Section 6.4.1.1 for AE reporting criteria for these seizure events.

The caregiver will be trained by the site with specific instructions beginning with the screening visit to ensure compliance in recording seizures. The seizure diary will be completed each day during 12 weeks of treatment beginning at screening and continuing through the EOT. Seizure diaries will be collected and reviewed by the investigator with the subject's caregiver for proper recording at the baseline, Week 6, and Week 12 (or EOT) study site visits. Seizure Identification Form and Diagnostic Review Forms (SIF/DRF) will be completed by site personnel for every eligible subject. This information will be faxed or emailed to The Epilepsy Study Consortium (TESC) for review and approval. The SIF/DRF will be used to ensure that the seizures are

classified accurately. SIF and DRF forms will be collected for patients who have enrolled/completed the study if feasible.

For the prospective baseline period, the seizure frequency (expressed as a 28-day frequency) will be calculated as

$$(\# \text{ of seizures}) / (\# \text{ of days seizures were assessed}) \times 28$$

Seizure frequency calculated through this method will be used to confirm the eligibility.

6.4.2.3 Vital Sign Measurements

Vital sign measurements will include blood pressure, temperature, heart rate, and respiratory rate. Measurement of vital signs should be attempted after the subject has been resting in a supine or sitting position for at least 10 minutes.

6.4.2.4 Physical Examinations

Height, weight, and head circumference will be measured as part of the physical examination, but height will be measured only at the screening visit. A physical examination will include a relevant general assessment of: general appearance; skin; head, eyes, ears, nose and throat; neck; lymph nodes; chest (including lungs); heart; abdomen; extremities; nervous system; and musculoskeletal system.

6.4.2.5 Exposure During Pregnancy and/or Lactation

OV101 should not be administered to pregnant or lactating females because the potential for adverse reactions to OV101 in pregnant females, fetuses, and nursing infants is unknown.

Pregnancy data will be collected during this study for all subjects. Exposure during pregnancy (also referred to as exposure in-utero) can be the result of either maternal exposure or transmission of drug product via semen following paternal exposure.

For all Ovid products, both in development or post-approval, exposure during pregnancy must be recorded and the subject followed until the outcome of the pregnancy is known (spontaneous miscarriage, elective termination, normal birth, or congenital abnormality), even if the subject discontinues study drug or discontinues from the study.

If a subject within this study or a subject's partner becomes pregnant while treated or exposed to study drug, the investigator must submit a pregnancy form to Ovid via the same method as SAE reporting. Pharmacovigilance will supply the investigator with a copy of a "Pregnancy Reporting

and Outcome Form/Breastfeeding.” When the outcome of the pregnancy becomes known, the form should be completed and returned to Ovid or Ovid Pharmacovigilance delegate. If additional follow-up is required, the investigator will be requested to provide the information.

Exposure of an infant to an Ovid product during breastfeeding must also be reported and any AEs experienced by the infant must be reported to Ovid Pharmacovigilance or designee via email or fax (Section 6.4.1.5).

Pregnancy is not regarded as an AE unless there is a suspicion that study drug may have interfered with the effectiveness of a contraceptive medication. However, complications of pregnancy and abnormal outcomes of pregnancy are AEs and may meet criteria for an SAE (such as ectopic pregnancy, spontaneous abortion, intrauterine fetal demise, neonatal death, or congenital anomaly). Elective abortions without complications should not be reported as AEs

6.5 Safety Monitoring Committee

An IDMC (Section 11.1.1) will provide safety monitoring. Oversight of the study conduct and IDMC will be provided by the Clinical Trial Steering Committee (CTSC; Section 11.1.2).

Routine pharmacovigilance oversight will be provided by Ovid Drug Safety.

6.6 Pregnancy

Female subjects who are of childbearing potential (defined as having experienced their first menarche) must agree to use either a highly effective or acceptable form of birth control during the study and for 30 days following the last dose of the study. Highly effective contraceptive methods are as follows:

- a. Combined (estrogen and progestogen containing) hormonal contraception associated with inhibition of ovulation:
 - Oral
 - Intravaginal
 - Transdermal
- b. Progestogen-only hormonal contraception associated with inhibition of ovulation:
 - Oral
 - Injectable
 - Implantable
- c. Intrauterine device

- d. Intrauterine hormone-releasing system
- e. Bilateral tubal occlusion
- f. Vasectomized partner
- g. Sexual abstinence

Acceptable birth control methods that result in a failure rate of more than 1% per year include:

- a. Progestogen-only oral hormonal contraception, where inhibition of ovulation is not the primary mode of action.
- b. Male or female condom with or without spermicide.
- c. Cap, diaphragm or sponge with spermicide.
- d. A combination of male condom with either cap, diaphragm, or sponge with spermicide (double barrier methods) are also considered acceptable, but not highly effective, birth control methods

For male subjects with women of child-bearing potential partners, there are no restrictions. Female subjects who have experienced menarche will undergo serum beta-human chorionic gonadotrophin (β -hCG) pregnancy testing at study site visits shown in Table 6–1 (as part of the sampling for clinical laboratory tests). Any female subject with a positive pregnancy test result at Screening must be excluded from the study. A serum β -hCG pregnancy test must be performed if any female subject is suspected of becoming pregnant during the study.

If pregnancy occurs at any time during the study, study drug must be discontinued immediately (or not started). Pregnancy is not regarded as an AE unless there is a suspicion that a study drug may have interfered with the effectiveness of a contraceptive medication. Any pregnancy that occurs during study participation must be reported using the same procedures as an SAE (Section 6.4.1.5) but using a clinical study pregnancy form. The pregnancy must be followed-up to determine outcome (including spontaneous miscarriage, elective termination, normal birth, or congenital abnormality) and status of mother and child, even if the subject is discontinued from the study. Pregnancy complications and elective terminations for medical reasons should not be reported as an AE or SAE. Spontaneous miscarriages must be reported as an SAE.

Any SAE occurring in association with a pregnancy, brought to the investigator's attention after the subject has completed the study and considered by the investigator as possibly related to the study treatment, must be promptly reported to Ovid Drug Safety.

6.7 Laboratory Analyses

The following clinical analytes will be assayed as safety assessments:

Hematology: hematocrit; hemoglobin; red blood cell count with indices (mean corpuscular volume, mean corpuscular hemoglobin, and mean corpuscular hemoglobin concentration); reticulocytes; white blood cell count and differential (neutrophils, lymphocytes, monocytes, eosinophils, and basophils) reported as percentages and absolute values; and platelets (platelet count, prothrombin time and partial thromboplastin time, international normalization ratio).

Clinical chemistry: albumin; alkaline phosphatase; blood urea nitrogen; gamma-glutamyl transferase; calcium; creatinine; glucose; cholesterol (high-density lipoprotein and low-density lipoprotein [calculated] and homogenous low-density lipoprotein); triglycerides; magnesium, phosphate; potassium; alanine aminotransferase; aspartate aminotransferase; lactate dehydrogenase; sodium; chloride; bilirubin (total, direct); total protein; uric acid; and creatine phosphokinase.

Pregnancy testing: Serum β -hCG for female subjects who have experienced menarche. Serum pregnancy testing will be conducted at screening and baseline. Serum pregnancy testing is recommended at subsequent visits; however, urine pregnancy testing is allowed if serum is not obtainable. If serum cannot be collected, the reason should be documented in the source document and, for sexually active female subjects, the results of the serum pregnancy test obtained at Visit 1 must be confirmed to be negative by the investigator before randomization.

6.8 Sample Collections

Blood samples collected from subjects will be forwarded to a central laboratory for analysis. Further details regarding sample collections and processing and specific testing can be found in the study manual (provided to study sites as a separate document).

All samples for clinical laboratory analysis will be collected as described in the study manual, according to the schedule of activities (Table 6–1). Samples for hematology and clinical chemistry will be used only for the evaluation of safety and tolerability.

Blood samples will be collected for clinical laboratory, safety assessments, [REDACTED]
[REDACTED] A total of up to 7 mL of blood is expected to be taken for laboratory measurements at

each of the screening, baseline, Week 6, and Week 12 visits. Total blood collected will not exceed 20 mL in a 30-day period. This is in accordance with the US Department of Health and Human Services, office for Human Research Protections recommendations of 3 ml/kg, up to 50 ml total within 8 weeks (Table 2 in Howie 2011).

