3.1 Study Design

[figure not shown]
This will be a Phase 3, randomized, double-blind, placebo-controlled, parallel-group study, conducted in clinic settings, to evaluate the efficacy and safety of OV101 in pediatric subjects with AS. Male and female subjects with a previous diagnosis of AS (with molecular confirmation) will be eligible for inclusion (Section 4.1). The study will comprise a screening period within the 28 days preceding Day 1; a visit on Day 1 for baseline assessments, the first dose of study drug, and sparse sampling of blood; subsequent doses of study drug taken each evening approximately 30 minutes before bedtime for 12 weeks starting on Day 2; and study site visits for efficacy and safety assessments over a 12-week treatment period. After the baseline visit, the study site visits will occur at Week 6 and Week 12 (end of treatment [EOT]). Phone safety visits will occur during up-titration of the study drug (Day 6 and Day 11). Unless a subject decides to participate in the ELARA open-label extension study, an end of study (EOS) phone safety visit will occur approximately 2 weeks after the last dose of study drug to assess safety and tolerability associated with discontinuation of treatment. Subjects eligible for and willing to enroll in the ELARA study will have the NEPTUNE EOT visit be their NEPTUNE EOS visit, and their NEPTUNE EOT visit will serve as their ELARA baseline visit. A subject will be considered to have completed the NEPTUNE study after completing the EOS visit. For NEPTUNE subjects participating in ELARA, the EOS visit that occurs approximately 2 weeks after the EOT will take place in the ELARA study only. The total duration of the study for a subject will be approximately 18 weeks. The schedule of activities for this study is fully presented in Table 6–1.

[figure not shown]

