Approximately 95 subjects will be enrolled in the study at approximately 15 study sites in the United States, Israel, Australia and/or Europe. Approximately 90 subjects 4 to 12 years old (inclusive) will be enrolled for both efficacy and safety assessments, and not more than 12 of these subjects will be enrolled at a study site (unless authorized by Sponsor). Random assignment of subjects for efficacy assessment (to either OV101 or placebo treatment in a 1:1 ratio) will be stratified by age at screening [9 to 12 years old (inclusive) and 4 to 8 years old (inclusive)] and by region (US and outside US). There will be at least 24 subjects per age group. Approximately 5 subjects 2 to 3 years old (inclusive) will be enrolled for safety [REDACTED] assessments only and will be assigned to treatment with OV101. Within each age group, dosing will be assigned based on body weight (Table 5–1).

[figure not shown]
For each subject, after informed consent is obtained (Section 9.3), screening assessments will be completed within the 28 days preceding Day 1 (baseline). On Day 1, eligible subjects will receive study drug capsules according to treatment code (sufficient to last until the Week 6 visit).

Caregivers/LARs will be provided an additional blister card in case of unexpected delays for study visits (e.g., inclement weather/flight delays). Study drug will be similarly dispensed at the Week 6 visit. Unused study drug will be collected and counted at Week 6 and 12.

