4.1.1 Inclusion Criteria

Each subject must meet all the following criteria to be enrolled in this study:

1. Is male or female and 2 to 12 years old (inclusive) at the time of informed consent.
2. Has a diagnosis of AS with molecular confirmation.
3. Has a CGI-S-AS score (Section 6.2.1.1) of 3 or more.
4. Meets the following age-appropriate body weight criterion:
 - a) Subjects 2 to 3 years old must have a minimum body weight of 9 kg.
 - b) Subjects 4 years and older must be between 17 kg and 64 kg (inclusive).
5. Has an LAR/caregiver capable of providing written informed consent and able to attend all scheduled study visits, oversee the administration of study drug, and provide feedback regarding the subject's symptoms and performance as described in the protocol.
6. Provides assent to the protocol (to the extent possible and in accordance with local institutional review board [IRB] and regulatory requirements). Subjects providing assent must do so at the same visit as LAR/caregiver written informed consent is provided.
7. Can swallow study drug capsules with water or ingest the contents of study drug capsules after sprinkling the contents of each capsule onto up to 1 teaspoon of low-fat semiliquid food.

8. If a subject is currently receiving a regimen of concomitant medications such as antiepileptic medication, gabapentin, clonidine, trazodone, melatonin, or a special diet regimen, that subject's regimen is stable for at least 4 weeks before Day 1 (first day of study drug administration) and will be maintained throughout the duration of the study (in the judgment of the investigator).
9. If a subject is a sibling in a family with multiple children diagnosed with AS, then only one of the siblings may enroll in study. The eldest eligible subject should be enrolled (investigator discretion may be used to enroll a younger sibling instead).
10. Has LAR(s)/caregiver(s) who agree not to post any of the subject's personal medical data or information related to the study on any website, message board(s), online support group(s), or social media site (e.g., Facebook, Instagram, Twitter, etc.) until notified that the study is completed.
11. Female subjects who are of child-bearing potential (defined as having experienced their first menarche) must agree to use either a highly effective or acceptable form of birth control during the study and for 30 days following the last dose of the study. Highly effective contraceptive methods are as follows:

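### Minor: the flat cap of 20 mL blood per 30 days does not by itself secure the cited limit of 3 mL/kg per 8 weeks below 13.3 kg, although the planned draws comply

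*Protocol*

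**What the plan says.** Protocol 6.8 (Sample Collections), repeated in the synopsis under Safety Assessments, makes three statements about volume:

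- The planned amount: "A total of up to 7 mL of blood is expected to be taken for laboratory measurements at" each of four visits (screening, baseline, Week 6 and Week 12).
- The cap: "Total blood collected will not exceed 20 mL in a 30-day period".
- A statement that this accords with "recommendations of 3 ml/kg, up to 50 ml total within 8 weeks".

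The same section sends the detail elsewhere: "Further details regarding sample collections and processing and specific testing can be found in the study manual".

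Section 4.1.1 sets the weights. For the youngest group, "Subjects 2 to 3 years old must have a minimum body weight of 9 kg"; from age 4 the range is 17 to 64 kg. Section 3.1 gives the size of the youngest group: "Approximately 5 subjects 2 to 3 years old (inclusive) will be enrolled for safety" assessments, all on OV101. Section 5.6 says they are not blinded. On timing, section 3.1 says: "The study will comprise a screening period within the 28 days preceding Day 1".

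Draws beyond the four planned ones are provided for in three places. Section 4.2.3 allows an uncertain or abnormal screening test to be repeated with the medical monitor's approval, and allows one rescreening. Exclusion criterion 3 in section 4.1.2 allows laboratory retests after consultation. The synopsis (Study Design) allows safety laboratory tests at unscheduled visits.

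**The concern.** The cap and the limit it is set beside are built differently. The cap has no weight term and runs over 30 days. The limit scales with weight and runs over 8 weeks. A site that checks only the cap before agreeing to a retest could satisfy it and still take a very light child past the limit the protocol says it follows. In the available text the cap is the only volume rule worded as a commitment, since the 7 mL per visit is merely expected. What is at stake is a safeguard for the smallest children in the study. Efficacy, power and type I error are not involved.

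**Working it through.** The documents show no calculation behind the accordance statement, so there is no figure to reproduce. The check compares the limit, the cap and the schedule.

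**Inputs.** Cap 20 mL per 30 days, limit 3 mL/kg to a maximum of 50 mL per 8 weeks (56 days), and 7 mL per planned visit (Protocol 6.8). Entry weights 9 kg (ages 2 to 3) and 17 kg (age 4 and over) (4.1.1). Screening from Day -28 to Day -1 (3.1). Day 1, Week 6 at Day 43 and Week 12 at Day 85 (SAP Table 2). There is no Day 0.

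**1. The cited limit.** Limit(w) = min(3w, 50) mL.
- At 9 kg: 3 × 9 = 27 mL.
- At 17 kg: 3 × 17 = 51, so the limit is 50 mL.

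**2. What the cap alone allows.** In any 56 days a rolling 30-day cap can be used in full twice, for example on Days 1 and 31: 2 × 20 = 40 mL.
- At 9 kg: 40 / 9 = 4.44 mL/kg.
- Weight at which 40 mL equals the limit: 40 / 3 = 13.3 kg.
- From 17 kg, 40 mL is below 50 mL, so the cap is sufficient for every randomized child.

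**3. What the schedule takes.**
- Screening on Day -13 to -1: screening, Day 1 and Day 43 fall within 56 days, so 3 × 7 = 21 mL, or 21 / 9 = 2.33 mL/kg. Room left at 9 kg: 27 - 21 = 6 mL.
- Screening on Day -28 to -14: at most 2 × 7 = 14 mL in any 56 days. Room left: 27 - 14 = 13 mL.
- In either case, at most 14 mL falls in any 30 days. The schedule meets both the cap and the limit.

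**4. What extra draws would do.** Their volumes are not given. I assume 0 to 7 mL each, with planned draws at 7 mL.

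| Extra draws | Most in 56 days | Most in 30 days | Over the limit |
|---|---|---|---|
| One 6 mL screening repeat (screening Day -13, repeat Day -6) | 27 mL | 20 mL | No |
| One unscheduled draw on Day 30 (screening Day -10), 5 / 6 / 7 mL | 26 / 27 / 28 mL | 14 mL | Only at 7 mL, below 28 / 3 = 9.33 kg |
| Screening repeat of 1 to 6 mL (Day -5) plus 7 mL on Day 30 (screening Day -10) | 29 to 34 mL | 15 to 20 mL | Below 9.67 kg (29 / 3) to 11.33 kg (34 / 3) |
| Same days, 2 + 4 mL / 3 + 4 mL | 27 / 28 mL | 16 / 17 mL | Only for 3 + 4 mL, below 9.33 kg |
| Rescreening alone (7 mL on Days -50, -20 and 1) | 21 mL | 14 mL | No |
| Rescreening with two 4 mL repeats (Day -50: 7, -45: 4, -20: 7, -15: 4, 1: 7) | 29 mL | 18 mL | Below 9.67 kg |
| Screening Day -21, one 7 mL extra on Day 49 | 21 mL | 14 mL | No |
| Screening Day -21, 7 mL extras on Days 49 and 74 | 28 mL | 14 mL | Below 9.33 kg |

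The cap is met in every row. A 7 mL screening repeat in the first row would reach 21 mL in 30 days, so the cap already blocks it. No row comes near 13.3 kg; that weight is the theoretical bound when the cap is fully used twice.

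**The case against.** The strongest reply is that nothing stated is wrong. The accordance sentence follows both the 7 mL plan and the cap, and the two together comply. Asking the cap alone to guarantee the limit asks more of it than the text claims. This stands, and it is why the point is one of wording.

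Three further replies have weight. First, screening repeats need the medical monitor's approval, eligibility retests need consultation, and rescreening is allowed once and only where it poses no safety risk. Second, the study manual and Table 6–1 may add volume controls; they are not available here, so their silence cannot be assumed. Third, unscheduled visits are for safety reasons, and a clinician would take a needed safety sample whatever the limit. That removes much of the force of the rows with an unscheduled draw. It does not remove the rescreening row, where no draw is driven by a safety event and the cap is still met at 29 mL in 56 days.

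A reader might infer that the protocol plans to take too much blood from the youngest children, or that its accordance statement is false. The documents support neither: the planned maximum is 21 mL against 27 mL at the lowest eligible weight.

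**Conclusion.** The point holds as a minor one. The planned collection complies at every eligible weight, but the flat cap does not secure the cited limit below 13.3 kg. Only some of the roughly 5 children aged 2 to 3 can be that light. In the cases worked through, the excess at 9 kg is 1 to 7 mL (28 to 34 mL against 27 mL), and it arises only when an extra draw is large or several are combined.

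This rests on four assumptions:

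- The 7 mL covers all blood taken at a planned visit. The text does not show whether the Day 1 sparse sampling is included, so it is not added.
- Extra draws are 0 to 7 mL each.
- The 30 days are a rolling period, which is the natural reading. If the cap were prorated, the bound would be 20 × 56 / 30 = 37.3 mL, or 12.4 kg. Under fixed consecutive blocks, 56 days could touch three (1 + 30 + 25 days) and allow 60 mL, above the 50 mL ceiling at any weight; I do not adopt that reading.
- No further control exists in the study manual or Table 6–1. If one does, the gap may already be closed in practice.

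The Pandemic Addendum also provides for an added on-site visit, but it needs written sponsor activation and is not used here.

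**What to change.** Optional, at the next amendment, in section 6.8 and the synopsis. Leave the cap of 20 mL per 30 days unchanged and without exception, and continue the sentence:

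*and, including repeat, rescreening and unscheduled study draws, will not exceed the lesser of 3 mL/kg or 50 mL in any 8-week period.*

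If the sponsor wants an exemption for medically necessary safety draws, it should attach only to the new 8-week limit. An exemption covering the whole sentence would make the 20 mL cap, which has no exception in the available text, conditional for all of the roughly 95 children.

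No planned draw changes, because 21 mL is below 27 mL. The cost is one clause in two places, carried in an amendment that needs IRB/IEC approval anyway (section 11.2.1), a running volume tally for a few children, and an occasional smaller or deferred non-urgent retest. It does not justify an amendment of its own. If the study manual already holds such a rule, a cross-reference to it would be enough.
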